## **5. TREATMENT OF SUBJECTS**

### **5.1 Investigational product/treatment**

The composition of the nutrition we will use is based on previous experimental findings and has already been tested in a human volunteer study (NCT00468507) showing that this nutrition is well-tolerated in healthy individuals. The lipid- and protein-rich nutrition contains 44 energy percent (en%) fat, 25en% protein, and 31en% carbohydrates. The protein fraction consists of intact casein, whey protein, and soy protein hydrolysate. The lipid fraction of the

feeding contains less than 5 weight percent omega-3 fatty acids. The nutrition provides 1 kcal/ml. The specific constituents of the feeding compositions are provided as Supplement.

## 6. METHODS

### 6.1 Primary endpoint

- Postoperative ileus

### 6.2 Secondary endpoints

- Anastomotic leakage
- Aspiration pneumonia
- Gastric volumes preoperatively
- Length of functional recovery
- The local and systemic inflammatory response
- Surgical complications
- Length of stay
- Intestinal barrier function and local inflammation in the gut
- Need for additional surgical, radiological or endoscopic interventions
- Need for ICU admission and total length of ICU stay
- Quality of life (EQ-5D-5L and EORTC-QLQ-C30 at baseline, after 3 and 6 months)
- Cost-effectiveness ratios (iMCQ and iPCQ at baseline, after 3 and 6 months)
- Composition of faecal microbiome

### 6.3 Randomisation, blinding and treatment allocation

After obtaining written informed consent patients will be randomly assigned to one of two groups by randomization software (TENALEA Clinical Trial Data Management System). The randomization list was generated by this computerized program using random blocks with maximum block size 6, stratified by operation location (colon or rectum) and operation type (laparoscopic or open). Blinded, study-specific enteral feeding systems are prepared and coded according to this list. A corresponding randomization website will be used that generates the sequential randomization number corresponding to the stratified randomization list upon randomization of a patient. All patients will receive a selfmigrating nasojejunal tube (Flocare Benchmark) one day before surgery. The position of the nasojejunal tube is controlled by abdominal X-ray at the day before surgery. Enriched enteral nutrition (Danone research™) is lead through a programmed Flocare enteral feeding pump. The pump is connected to an opaque branched enteral feeding system (produced by ECM bv, Gemert, the Netherlands) that is connected both to the nasojejunal tube and to a sealed container.

Three hours before surgery the pump is started to administer nutrition in standardized amounts.

Patients are either allocated to the experimental group, in which the blinded branched enteral feeding system leads the enteral nutrition via the nasojenunal tube to the patient. Via this route, the patients in the experimental group will receive the enteral nutrition just before, during and directly after surgery.

In patients allocated to the control group, the blinded branched enteral feeding system leads the enteral nutrition to the container. Consequently, when the feeding pump starts just before surgery, patients in the control group do not receive the nutrition. In both groups, the pump with enteral nutrition is stopped 6 hours after surgery and normal intake is resumed. The used enteral feeding systems are stored by an independent person, to create a checkpoint whether allocation to intervention and control group happened correctly.

The study is blinded for the patient, the surgeon and nursing staff. A protocol explaining the study design and blinding is attached (Appendix A)

#### **6.4 Study procedures**

Blood samples will be collected at several predefined moments in relation to the moment of incision. Based on previous clinical trials in which we have measured the inflammatory response, these time points will be at 4h, 24h and 48h after surgery. Tissue samples from the resected colorectal segment are collected during the surgical procedure for immunohistochemistry, Western Blot and PCR analysis. When collected, all samples are stored at -80°C until further analysis. The inflammatory response is measured by analysing the blood plasma and tissue samples for inflammatory mediators (amongst which TNF-alpha and interleukins such as IL-6 and IL-8). This will be done for a large part using commercially available enzyme linked immune assays (ELISA) and by PCR. Also, the inflammatory response and tissue damage parameters will be monitored in peritoneal lavage fluid. For this, 500cc saline will be installed just after opening of the abdomen and at the end of surgery.

Intestinal tissue damage is measured by analysis of several markers for intestinal damage in blood and tissue samples such as Intestinal Fatty acid Binding Protein (I-FABP). Patient characteristics and clinical parameters are registered in an electronic database. All surgical complications are classified using the Clavien-Dindo classification.

Postoperative ileus will be measured clinically in a patient diary (Supplement) based on parameters such as time to first flatus and first defecation, which are the most suitable according to the available literature. Furthermore, gastric motility will be assessed by ultrasound of the gastric antrum just before and following a standardized meal after 15 minutes and 90 minutes as previously performed (trial M11-1102, CCMO NL25588.096.08).

Previous studies have shown that antrum measurements are representative for determining gastric emptying and thereby gastric motility. This ultrasound measurement will be performed by a specifically trained M.D.

All results of these measurements are registered in an electronic database. Patients are discharged according to known criteria as in ERAS/ fast-track surgery.

Quality of life is measured via a checklist (EQ-5D-5L and EORTC QLQ C-30) for cancer patients pre- and postoperatively. Long-term outcome parameters such as local recurrence, overall and cancer-specific survival will be registered in a database. Healthcare costs, costs to patients and family are measured at the individual level using data from registration systems of the hospitals and patient questionnaires (including adapted version of the iMTA Medical Consumption Questionnaire (iMCQ) and the iMTA Productivity Cost Questionnaire (iPCQ)).

Preoperatively and on the fourth postoperative day, a total of two fecal samples will be collected. Using the E-Nose, composition of the luminal microbiome will be determined.

## **6.5 Withdrawal of individual subjects**

Subject can leave the study at any time for any reason if the wish to do so without any consequences. The investigator can decide to withdraw a subject from the study for urgent medical reasons.

## **7. NUTRITION**

### **7.1 Perioperative enteral nutrition**

Perioperative administration of enteral nutrition is a new concept. Restriction of food and fluid intake prior to general anaesthesia has long been applied as a method to reduce the risk of regurgitation of gastric contents. Increasing evidence has been build over the last years that this insight may be out of date and not evidence-based. A Cochrane review showed that it was safe to apply a shortened fluid fast (of 2 hours before surgery) and that such a regimen did not results in an increased risk of aspiration, regurgitation or related morbidity compared with the standard 'nil by mouth from midnight' fasting policy. Permitting patients to drink water preoperatively even resulted in significantly lower gastric volumes. Since perioperative nutrition is a new concept the risk of aspiration pneumonia needs to be monitored closely. For aspiration pneumonia gastric volume and acidity are important. Emergency patients with larger initial gastric volumes are more susceptible for pneumonia.

In this trial nutrition will be administered postpylorically thereby reducing gastric volumes. All patients will receive a selfmigrating nasojejunal tube (Flocare Bengmark) one day before

surgery at the ward. The position of the nasojejun tube will be controlled by X-ray at the night before surgery. Enteral nutrition will be administered postpylorically in low amounts.

The lipid rich nutrition provides 1 kcal/ml. The rate of infusion will be determined according to the re-evaluated Harris and Benedict equation of Roza and Shizgal. In this way a rate of 1,5 ml/ minute is generally infused.

The nutrition is administered during a timeframe of 3 hours before, until 6 hours after surgery. Preoperatively, patients receive standard of care with a fast for solid (oral) food of 6 hours and a (oral) fluid fast for 2 hours before administration of the nutrition by the nasojejun tube. To minimize the risk of aspiration pneumonia the stomach will be emptied by a gastric tube before start of surgery. In a human volunteer study the nutrition was well tolerated and did not lead to unwanted side-effects. Gastric volumes will be measured when the stomach is emptied, before start of surgery at the operating room. Based on the above, the risk of administering perioperative nutrition is minimized by given the nutrition postpylorically, in a low volume and assuring an empty stomach before intubation.

## **8. PATIENT SAFETY, DATA MONITORING**

This prospective randomized clinical trial will be conducted according to the rules of Good Clinical Practice (GCP). An independent data safety monitoring board will be appointed by the investigators that will evaluate all complications and monitor patient safety. Specifically, the aspect of safety of perioperative administration of enteral nutrition will be closely monitored. The clinical trial will be conducted at the Catharina Hospital in Eindhoven.

### **8.1 Adverse events (AEs)**

Adverse events are defined as any undesirable experience occurring to a subject during the study, whether or not considered related to the intervention. All adverse events reported spontaneously by the subject or observed by the investigator or his staff will be recorded.

### **8.2 Serious adverse events (SAEs)**

A serious adverse event is any untoward medical occurrence or effect that at any dose:

- results in death;
- is life threatening (at the time of the event);
- requires hospitalisation or prolongation of existing inpatients' hospitalisation;
- results in persistent or significant disability or incapacity;
- is a congenital anomaly or birth defect;
- Any other important medical event that may not result in death, be life threatening, or require hospitalization, may be considered a serious adverse experience when, based upon

appropriate medical judgement, the event may jeopardize the subject or may require an intervention to prevent one of the outcomes listed above.

Infectious complications and serious complications as a result of the operation that lead to prolongation of the patients' stay in the hospital will be registered as a SAE

The investigator will report the SAEs through the web portal ToetsingOnline to the accredited METC that approved the protocol, within 15 days after the sponsor has first knowledge of the serious adverse reactions.

SAEs that result in death or are life threatening should be reported expedited. The expedited reporting will occur not later than 7 days after the responsible investigator has first knowledge of the adverse reaction. This is for a preliminary report with another 8 days for completion of the report.

### **8.3 Annual safety report**

The sponsor/investigator will submit a safety report to the METC once a year. This report consists of a list of all suspected serious adverse reactions and a report concerning the safety of the subjects, consisting of a complete safety analysis and an evaluation of the balance between the efficacy and the harmfulness of the medicine under investigation.

### **8.4 Follow-up of adverse events**

All AEs will be followed until they have abated, or until a stable situation has been reached. Depending on the event, follow up may require additional tests or medical procedures as indicated, and/or referral to the general physician or a medical specialist.

SAEs need to be reported till end of study within the Netherlands, as defined in the protocol

### **8.5 Data and safety monitoring board**

An independent data and safety monitoring board (DSMB) will evaluate the progress of the trial and will examine safety variables. SAE's need to be reported to the principal investigator within 24 hours, some SAE's will be specified such as: re-intervention, respiratory failure, aspiration pneumonia, myocardial infarction, transfer to the ICU for any reason. Per 10 patients, individualized patient data will be presented to the DSMB. After full explanation of the data presented, the members of the DSMB discuss the consequences of the data presented separately. Besides the assessment of SAE's and AE's a safety analysis will be made after inclusion of 40 patients. In this analysis there is a special focus on gastric

volumes which will be compared as well as incidence of aspiration pneumonia. Adverse events will be listed and discussed with the DSMB. The outcome of the meeting of the DSMB will be discussed with the research group. The outcome will also be sent to the Medical Ethics Committee. All possible adverse events will be reported to the Central Committee on Research involving Human Subjects (Centrale Commissie Mensgebonden Onderzoek (CCMO)) and the IRB using the online module <https://toetsingonline.ccmo.nl>.

The DSMB includes:

1. Prof [name], Emeritus [name]
2. Dr. [name], Gastroenterologist
3. Dr. [name], Intensive Care Medicine
4. Dr. [name], Epidemiologist.

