## 1. SUMMARY

**Rationale:** Postoperative ileus and anastomotic leakage are complications associated with short-term morbidity and mortality following colorectal surgery. Based on experimental studies, we hypothesize that enriched enteral nutrition shortly before, during and early after colorectal surgery reduces inflammation by stimulation of the autonomic nervous system and thereby postoperative ileus (POI) and anastomotic leakage.

**Objective:** The main objective is to investigate the effects of perioperative nutrition on postoperative ileus and anastomotic leakage in patients undergoing colorectal surgery.

**Study design:** A prospective randomized double blinded controlled trial

**Study population:** Patients undergoing segmental colon/ rectum resection with a primary anastomosis for colorectal cancer >18 years.

**Intervention:** Perioperative nutrition via a nasojejunal tube.

**Main study parameters:** Main clinical outcome parameters are postoperative ileus and anastomotic leakage. Risk of aspiration pneumonia is closely monitored. Before intubation, gastric volumes are measured and the stomach is emptied. The inflammatory response will be quantified by standard assays including Enzyme Linked Immunosorbent Assay (ELISA) and Polymerase Chain Reaction (PCR). Mediators important in the pathogenesis of POI will also be measured in peritoneal lavage fluid. Clinical parameters are prospectively registered in a database and complications are classified using the Clavien-Dindo classification of surgical complications. Other parameters include intestinal barrier integrity and local inflammation in the intestine (measured by PCR and immunohistochemistry). Long-term outcome parameters such as local recurrence, overall and cancer-specific survival will also be registered.

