**Nature and extent of the burden and risks associated with participation, benefit and group relatedness:**

All patients will receive a selfmigrating nasojejunal tube (Flocare Bengmark) one day before surgery. The position of the tube is checked via X-ray the same day. Via a specially designed blinded setup (produced by ECM bv, Gemert) patients in the intervention group receive enriched enteral nutrition in low amounts before, during and directly after surgery until oral intake is started. Patients in the control group do not receive nutrition and get a standard preoperative fast until standard oral intake is commenced.

Blood samples will be collected at several predefined moments in relation to the moment of incision. Furthermore, gastric emptying will be assessed via ultrasound before and following a standard meal at day 2 postoperatively. This intervention may benefit the patient by reducing postoperative complications and enhancement of recovery.

Peritoneal lavage is performed at the start of surgery and at the end of surgery. Also gastric content is measured during surgery. It is expected that these procedures will be no burden for the patient.

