**Operatie**

Datum operatie: \_\_\_ / \_\_\_ / 20\_\_\_ Operateur: \_\_\_\_\_

Starttijd operatie: \_\_\_:\_\_\_ uur

Eindtijd operatie: \_\_\_:\_\_\_ uur

Aspiratie bij intubatie/OK:  Nee  Ja

Procedure:  Open  Laparoscopisch  
 conversie

Type OK:  Hemicolectomie links  
 Hemicolectomie rechts  
 Low Anterior resectie  
 Ileocoecaal resectie  
 Sigmoidresectie  
 Rectosigmoidresectie  
 Transversum resectie  
 Overig, namelijk \_\_\_\_\_

iORT  Nee  Ja

Stoma aangelegd:  Nee  Ja  
 Eindstanding / dubbelloops  
 Ileostoma / colostoma

Epiduraal:  Nee  Ja  
 Start hoeveelheid: \_\_\_\_\_  
 Tijdens OK hoeveelheid: \_\_\_\_\_

Noradrenaline:  Nee  Ja hoeveelheid: \_\_\_\_\_

Maagvolume preoperatief: \_\_\_\_\_ ml

Intra-operatief bloedverlies: \_\_\_\_\_ ml

Vocht toegediend tijdens OK: \_\_\_\_\_ ml

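### The CRF records aspiration at intubation or in theatre, but no between-arm comparison of it is planned, and the gastric volume that is compared precedes most of the feed

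*Combined protocol and SAP*

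**What the plan says.** Section 12 names aspiration pneumonia as the potential risk of the intervention, and section 4.4 defines it as lung inflammation that follows aspiration of material. For the analysis after 40 patients, section 8.5 puts a special focus on gastric "volumes which will be compared as well as incidence of aspiration pneumonia". This comes in addition to the assessment of AEs and SAEs, and adverse events are to be listed and discussed with the DSMB.

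The endpoint list in section 6.2 contains aspiration pneumonia and preoperative gastric volume. Section 9 compares the primary and secondary endpoints between the groups and gives risk ratios with 95% confidence intervals.

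The CRF (Appendix III, Operatie) has a yes/no item, "Aspiratie bij intubatie/OK", and a single preoperative gastric-volume field in ml. Under the postoperative course it has a gastric-tube item with in and out dates.

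On feeding, section 7.1 says "The nutrition is administered during a timeframe of 3 hours before, until 6 hours after surgery" and "In this way a rate of 1,5 ml/ minute is generally infused". On the timing of the volume reading, the same section says "Gastric volumes will be measured when the stomach is emptied, before start of surgery at the operating room", and the summary says "Before intubation, gastric volumes are measured and the stomach is emptied". The burden-and-risks text, however, says "Also gastric content is measured during surgery", and section 12.1, item j, also places the measurement during surgery.

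**The concern.** By the protocol's own definition, aspiration is the step that comes before aspiration pneumonia. The trial collects that step but plans no comparison of it. If more fed patients aspirated and few went on to pneumonia, the excess would appear only as single entries in adverse event listings, with no tabulation by arm.

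The other compared measure, gastric volume, is a single preoperative reading. It cannot reflect what happens during the rest of the feed. The trial could report no difference in gastric volume or aspiration pneumonia while an imbalance in recorded aspirations sat untabulated in its own data.

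**Working it through.** **1. Which items are compared**

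| Item | In CRF | Endpoint in 6.2 | Named for comparison in 8.5 | Covered by section 9 |
|---|---|---|---|---|
| Aspiration pneumonia | yes | yes | yes | yes |
| Gastric volume | one preoperative field | yes, preoperative | yes | yes |
| Aspiration at intubation or in theatre | yes/no, under Operatie | no | no | no |
| Postoperative gastric tube | yes, with dates | no | no | no |

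The endpoint for surgical complications in section 6.2 does not clearly take in the aspiration item. The CRF places that item in the operation block, apart from the postoperative complications.

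**2. Share of the feed given by the start of surgery**

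The plan states no such share, so there is no figure of its own to reproduce. Inputs from section 7.1: feeding for 3 h before surgery, through surgery, and for 6 h after, at about 1.5 ml/min, which is 90 ml/h. The documents give no expected operating time; the CRF only records it, from "Starttijd operatie" and an end time. Let d be the operating time in hours and assume a constant rate.

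- Feed before surgery: 3 × 90 = 270 ml.
- Whole course: 90 × (9 + d) ml.
- Share before surgery: 3 / (9 + d). The rate cancels.

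| d (assumed) | Whole course | Share before surgery |
|---|---|---|
| 1 h | 900 ml | 30% |
| 2 h | 990 ml | 27% |
| 3 h | 1080 ml | 25% |
| 4 h | 1170 ml | 23% |
| 6 h | 1350 ml | 20% |

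The limit as d goes to 0 is 3/9, or 33%. The share is therefore below one third for any operating time, and that statement needs no assumed duration.

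If the volume were instead read during surgery, the share would lie between 3/(9 + d) and (3 + d)/(9 + d). That is 27–45% for d = 2 (3/11 to 5/11) and 23–54% for d = 4 (3/13 to 7/13). The conflict in timing therefore changes what the volume result means.

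**3. What a comparison could show**

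Assume about 20 patients per arm at the 40-patient analysis. Fisher's exact test, two-sided, gives p = 0.106 for 4 versus 0 events and p = 0.047 for 5 versus 0. With no events in 20, the one-sided 95% upper limit is 1 − 0.05^(1/20) = 13.9%. At the planned 140 per arm, no events would give 1 − 0.05^(1/140) = 2.1%. The early comparison can only describe; the final one is more informative.

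**The case against.** The strongest reply is that safety oversight is wider than the two compared measures. The 40-patient analysis is made besides AE and SAE review. Section 8.5 also sends individual patient data to the DSMB per 10 patients and specifies respiratory failure and ICU transfer as SAEs. Surgical complications and ICU need are compared as secondary endpoints, so an aspiration with consequences could reach a comparison by another route. The preoperative reading also looks deliberate, because the stated safeguard in section 7.1 is an empty stomach before intubation.

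Most of this stands, and it limits the point. A reader might infer that direct signs of the named harm are never compared. The documents do not support that: the named harm is aspiration pneumonia, and its incidence is compared both at 40 patients and at the end. A reader might also infer that the safety review uses only two measures. Section 8.5 calls them a special focus, which is weaker. What remains is that listing events is not tabulating them by arm, and an aspiration that did not become pneumonia need not fall under any of the specified SAEs.

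A second reply is that the CRF item covers intubation and theatre only, so it says nothing about the 6 postoperative hours. That is correct and must be stated with the result. A third is that 40 patients are too few. That applies equally to aspiration pneumonia, which the plan does compare; it argues for descriptive reporting, not for leaving the item out.

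**Conclusion.** The point holds as a cheap improvement to the safety analysis. The aspiration item is collected, bears directly on the one risk the protocol singles out, and has no planned between-arm comparison. The preoperative gastric volume precedes more than two thirds of the feed for any operating time, given a constant rate and a reading by the start of surgery. The figure of 23–27% also needs an assumed operating time of 2–4 h.

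The gain in events cannot be sized, because the documents give no rate for aspiration or for aspiration pneumonia.

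It is tempting to treat the postoperative gastric tube as a second uncompared sign of aspiration. The documents do not support that. Section 7.1 has every stomach emptied by a gastric tube before surgery, and the CRF field cannot separate a tube left in place from one put back later. Tube use also reflects ileus, which the feed is meant to reduce.

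**What to change.** In sections 8.5 and 9, add a comparison of the existing CRF aspiration item, at the 40-patient analysis and at the end. Report it by arm, alone and combined with aspiration pneumonia as 'any aspiration event', with counts and risk differences with exact 95% intervals. The risk ratio of section 9 is undefined if the control arm has no events. Label the 40-patient result descriptive, and state that the item does not cover the 6 h of postoperative feeding.

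Either leave postoperative gastric-tube use out of the comparison, or show it as a separate descriptive row limited to tubes with an in-date after the day of surgery.

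Reconcile the timing of the gastric volume measurement. The summary, section 7.1 and the CRF place it before intubation or surgery; the burden-and-risks text and section 12.1 place it during surgery. Then state which part of the feed the volume result covers.

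The cost is a few lines of text and one or two more safety rows, with no new data or staff. The downside is that these rows will hold very few events and wide intervals, so a chance imbalance could be over-read.
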